## **Participant Selection**

### **Recruitment**

Women will be recruited from the community through flyers (Appendix A). They will call into a study phone line or respond through Be Involved at which time they will be screened for their initial eligibility using a telephone screener (Appendix B). Women who are eligible and willing to participate, will come to the PHS Research Center in Piedmont Plaza 1 or the Center for Integrative Medicine in Piedmont Plaza II to be consented and complete baseline questionnaires or sent materials via mail or email to complete. They will be sent home or given a hot flash diary to complete for two weeks in order to confirm a sufficient number of hot flashes for study eligibility. After two weeks, women will mail back their diaries and continue to record their daily hot flashes until they are notified by study staff of their eligibility, within a week of receiving the diary.

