### **Secondary Measure**

- **Pittsburgh Sleep Quality Index (PSQI):** Sleep will be assessed using the PSQI, a well validated commonly used self-report sleep measure. The PSQI includes 19 questions on sleep quality in the last month. It provides an overall sleep quality score and sub-scores for subjective quality, latency, duration, efficiency,

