**Study Plan****Design**

We will conduct a non-randomized study of 24 peri or postmenopausal women aged 45-60 experiencing at least 4 hot flashes/night sweats/day on average to evaluate their hot flashes/night sweats while using the cooling mattress pad for 8 weeks. The device consists of a mattress pad that is placed between a person's mattress and fitted sheet that is connected to a cube that is filled with water and kept next to the bed. Participants can regulate the temperature of the cooling mattress pad by adjusting the temperature of the water that flows from the cube to the mattress pad. This is a totally non-invasive device.

Women will be recruited from the community through advertisements and initially screened over the telephone. They will be screened for age, menopause status, and average number of hot flashes per day. Those women who are eligible based on the telephone screen, will be invited to come to the Public Health Sciences (PHS) Research Center in Piedmont Plaza 1 or the Center for Integrative Medicine in Piedmont Plaza II for a baseline interview. At that time they will provide informed consent to participate in the study, complete several

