## REST: Reducing the Experience of Menopausal Symptoms through Temperature

questionnaires, and sent home with a 2-week diary to confirm their eligibility with respect to number of hot flashes/night sweats. If it is not possible for the participant to come to one of these locations, the baseline questionnaire and consent will be sent to the participant to be completed at home and mailed back. Two copies of the consent form will be sent to the participant. After received, a study team member will speak with the participant to present the elements of consent, the content of the study, and answer any questions. At the end of the discussion, the participant will be advised to sign and date one form and return it. The second form should be kept by the participant for documentation. Upon receipt of the signed form, the study team member will sign and date with the current date, and add a note detailing the date discrepancy.

We will ask participants to keep a record of their hot flashes throughout the day by either using a counter app on their phone or maintaining a paper log. After two weeks, women will mail in their diaries and continue to record their daily hot flashes until they are notified by study staff of their eligibility, within a week of receiving the diary.

If still eligible based on the 2-week diary, participants will return to the PHS Research Center to receive a cooling mattress pad and container of distilled water (used to fill cooling mattress pad) to take home and use for the next 9 weeks. If it is not possible for the participant to return to the Research Center, the Chilipad will be delivered to the participant at a mutually agreed upon location. We will allow one week for women to determine the optimal temperature of the cooling mattress pad and the next 8 weeks for the data collection of hot flashes/night sweats while using the cooling mattress pad. Some participants may be away from home and unable to use the cooling mattress pad while participating in the study. We will ask that participants indicate on the Hot Flash Diary whether or not they used the cooling mattress pad the prior night and continue tracking their hot flashes/night sweats even if they did not use the mattress pad.

Participants will mail in their completed Hot Flash Diary every two weeks in a pre-stamped and pre-addressed envelope to ensure that data is being consistently recorded.

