## **Statistical Considerations**

### **Analytical Plan**

Our primary outcomes of interest will be change in number of daily hot flashes (total, daytime, and nighttime) over the eight week period. We will model our outcome in both absolute terms (average number of daily hot flashes each week) as well as in terms of percentage change in average daily hot flashes measured from baseline. We will first conduct a simple t-test on the difference in average number of daily hot flashes at baseline and eight weeks to see if this average difference is significantly different from the null value of zero. We will also conduct repeated measures models with time included as ordinal week (0-9) and the dependent variable pertaining to average daily number of hot flashes for each week or percent change in average daily number of hot flashes for each week. In the simplest repeated measures models we will examine whether the parameter estimate for week is significantly different from zero. We will also examine the effects of covariates such as age and menopause status to determine which are significantly associated with the outcomes, and to estimate an adjusted (least squares mean) outcome measure that will serve as an accurate comparison to our historical control (see below).

Secondarily, we will model the continuous outcome of the total PSQI sleep score, as well as the subscores, using a similar repeated measures approach to that described above

In addition to examining, within our sample of cooling mattress pad users, the question of whether symptoms (hot flashes, sleep disturbance) improve over time, we will also compare any observed improvements with those found in our control group from the Acupuncture in Menopause (AIM) Study to see if cooling mattress pad users experienced significantly different levels of change over time compared to an historical control. (We note that in our AIM control group, there was on average an approximately -3.3% decline in average number of daily hot flashes from baseline to week 8, and there was an increase of .49 in total score on the PSQI over the same period.)

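### The only pre-treatment PSQI is completed around consent, at least 2 weeks before the pad starts, so pre-pad change in sleep is counted as pad effect and cannot be estimated

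*Combined protocol and SAP*

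**What the plan says.** Objective 2 concerns sleep, and Study Outcomes names the PSQI as the only secondary outcome. The Measures Timeline marks it at baseline and at follow-up and nowhere else. Secondary Measure states: "The PSQI includes 19 questions on sleep quality in the last month". It treats scores above 5 as poor sleep, so a rise is a worsening.

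The order of events comes from Recruitment and from Design:

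- Eligible women attend "to be consented and complete baseline questionnaires or sent materials via mail or email to complete". Design says of the baseline interview: "At that time they will provide informed consent to participate in the study, complete several" and, continuing overleaf, "questionnaires, and sent home with a 2-week diary to confirm their eligibility". Women who cannot attend complete the forms at home.
- "After two weeks, women will mail in their diaries and continue to record their daily hot flashes". The eligibility decision comes within a week of the diary's receipt.
- Eligible women then collect the pad, or have it delivered, and use it for 9 weeks: one to find a temperature and eight for data collection. Follow-up questionnaires come at the end.

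Under Analytical Plan, the PSQI is modelled "using a similar repeated measures approach to that described above"; the hot-flash model it refers to codes time as weeks 0 to 9. The observed change is also set against the AIM control group, in whom hot flashes were measured from baseline to week 8 and "there was an increase of .49 in total score on the PSQI over the same period". The section mentions neither the pad-free weeks nor the length of the PSQI interval.

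**The concern.** The first PSQI describes the month before a woman consented, not the time just before she received the pad. Whatever happens to her sleep between volunteering and hand-out enters the before-after difference. Women who volunteer when their symptoms are bad may improve without treatment; equally, sleep may go on worsening, as it did on average in the AIM controls. With no concurrent control arm, nothing absorbs this change. With no PSQI at pad start, nothing measures it.

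The AIM comparison is the only external reference for sleep, and as written it sets a change over at least 11 weeks beside one described as running to week 8.

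**Working it through.** **Inputs.** Diary before the pad: 2 weeks (Design). Decision: 0 to 1 week after the diary is received (Recruitment, Design). Postage and scheduling of hand-out: not stated. Pad use: 9 weeks (Design). AIM: +0.49, baseline to week 8 (Analytical Plan).

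**The plan's own timing figure.** The Measures Timeline gives 11 weeks of daily diary, which is 2 + 9. This reproduces, and allows nothing for postage, decision or scheduling.

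**Lead of the baseline PSQI over the pad** = diary + decision + postage and scheduling.
- Same-day decision: 2 + 0 = 2 weeks, plus unstated times.
- Full week to decision: 2 + 1 = 3 weeks, plus unstated times.

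**PSQI interval** = lead + 9.
- 2 + 9 = 11 weeks; 11/8 = 1.38 times AIM's stated interval.
- 3 + 9 = 12 weeks; 12/8 = 1.50 times.

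**Pad-free share** = lead / interval: 2/11 = 18%; 3/12 = 25%.

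**Illustration with an assumption.** Suppose postage plus scheduling takes 0.5 week with an immediate decision, up to 1.5 weeks with a full week to decision. The lead is then 2.5 to 4.5 weeks, the interval 11.5 to 13.5 weeks, and the pad-free share 2.5/11.5 = 22% to 4.5/13.5 = 33%. The documents do not give these delays.

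**Recall windows, taking a month as 30 days.** Nine weeks is 63 days, so the follow-up recall starts on about day 63 - 30 = 33 of pad use. It lies wholly within the pad period and after the temperature-setting week. The baseline recall lies wholly before the pad. The pad-free weeks fall between the two windows.

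**Scale only.** If the AIM drift were linear in time:
- 0.49 x 11/8 = 0.67
- 0.49 x 12/8 = 0.735

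The excess over 0.49 is 0.18 to 0.245 points. As a share of the benchmark (38% to 50%) it merely restates the interval ratio and is not separate evidence. Untreated REST women would be expected to worsen by 0.67 to 0.735 but would be compared with 0.49, so this mechanism works against the pad.

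**The case against.** This is a single-arm pilot seeking preliminary evidence, and giving questionnaires before an eligibility diary is an ordinary design choice. The primary outcome and the sample size calculation are untouched. The documents give no PSQI standard deviation, so nothing shows that a few tenths of a point would matter with 24 women. All of this stands, and it limits how serious the point is.

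Four stronger readings are tempting, and the documents do not support them:

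- **That the pad-free weeks dilute the on-pad score.** They do not: the follow-up recall month contains pad weeks only, apart from nights away. The fault is in the starting point.
- **That the AIM comparison is shown to be mismatched.** The documents do not say whether AIM's baseline PSQI preceded a run-in of its own. If it did, the elapsed times could be similar, and moving REST's baseline to hand-out could create a mismatch.
- **That the sleep result is biased in favour of the pad.** Regression to the mean would favour it; linear AIM drift would count against it. The net direction is unknown.
- **That repeated measures modelling of the PSQI is an error.** A model with two occasions is valid and allows covariates. It simply cannot separate pre-pad from on-pad change. Nor is it a fault in itself that the PSQI and diary baselines cover different periods, since no joint analysis is planned.

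What survives is the within-sample problem, which does not depend on AIM: change before the pad is attributed to it and cannot be checked.

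**Conclusion.** The point holds as a design weakness with a cheap remedy. From the documents alone, the baseline PSQI precedes the pad by at least 2 weeks and the change spans at least 11 weeks. The upper ends of 3 and 12 weeks assume a full week to the decision, and unstated postage and scheduling come on top. For women who complete baseline forms at home the lead may be longer.

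The size of the resulting bias is unknown because REST collects nothing from which to estimate it. The linear-drift figure rests on one group mean and an assumed straight line, and should not be read as an estimate of bias. Whether the AIM interval truly differs remains open until the sponsor states when AIM's baseline PSQI was taken.

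**What to change.** 1. Add a PSQI at pad hand-out to the Measures Timeline, completed before first pad use. Where the pad is delivered, have it completed at or before delivery, so that it is not filled in after use has begun.
2. In the Analytical Plan, take the within-sample PSQI change from the hand-out score to follow-up (9 weeks), and report the consent-to-hand-out change as a pre-pad reference.
3. State when AIM's baseline PSQI was taken relative to any run-in. For the AIM comparison, use whichever REST baseline matches that timing, show the other as a sensitivity analysis, and give both intervals.

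**Cost.** One extra 19-item form at a contact that already takes place, and small edits to the table and text. The recall months overlap: with a lead of 14 to 21 days and a 30-day month, 16 to 9 of the 30 days in the hand-out form's recall also fall in the consent form's (53% to 30%), and fewer with a longer lead. The pre-pad change is therefore only a rough reference.

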### Sample Size

This is a single site, single arm pilot study designed to obtain preliminary evidence that the cooling mattress pad can help reduce hot flashes and night sweats. We will compare results to historical controls from a previous study. Based on this previous study, we estimate that women recruited to our sample will be experiencing, on average, approximately 10 hot flashes at baseline. The average decline in number of daily hot flashes over an 8 week period in the control arm of this study was 0.36 (standard deviation 2.85). In comparison to the 0.36 fewer hot flashes on average in the absence of intervention (i.e., null hypothesis), we will be able to detect in our sample of 24 a decline of 2.1 in absolute number of average daily hot flashes from baseline to week 9, with 80% power and a two-tailed alpha of 0.05. We note that the ‘detectable’ anticipated decline of 2.1 in number of hot flashes (or just over 20% decline from baseline) is a conservative estimate; in our previously-sited study, a 35% decline in number of hot flashes over 8 weeks has been observed.

### Covariates

In addition to sociodemographics (Appendix I) (age, education, marital status, employment status), the following covariates will be assessed:

- **Symptom Sensitivity** is a measure of symptom sensitivity or amplification. The Somatosensory Amplification Scale (SSAS) is a 10-item questionnaire that assesses sensitivity to a range of uncomfortable bodily sensations and physiologic states which are not typically symptoms of disease. The SSAS has been shown to prospectively predict persistence of hypochondriacal symptomatology in transient hypochondriacal patients. This measure has been shown to be a strong predictor of vasomotor symptom reporting. It is included as a covariate because it is highly related to symptom reporting and symptom sensitivity may be an important variable related to treatment efficacy (Appendix J).
- **Health history and current medications.** At the baseline visit, participants will be asked to bring in all medications, vitamins, and herbal supplements they are currently taking so that these can be recorded (Appendix K). Medications will again be assessed at follow-up (Appendix O).
- **Health behaviors** will include standard questions on smoking and physical activity. Active *smoking* will be ascertained from the American Thoracic Society questions, *Physical activity* will be measured using 3 items we have used in previous studies (Appendix L). Change in health behaviors will be assessed (Appendix N)

## **Appendices**

Appendix A	Study Flyer
Appendix B	Telephone Screener
Appendix C	Hot Flash Diaries
Appendix D	Pittsburgh Sleep Quality Index (PSQI):
Appendix E	The Hot Flash Related Daily Interference Scale (HFRDIS)
Appendix F	Center for Epidemiologic Studies Depression (CESD-10)
Appendix G	General Anxiety Disorder (GAD-7)
Appendix H	Health-Related Quality of Life (HRQL)
Appendix I	Sociodemographics
Appendix J	Somatosensory Amplification Scale (SSAS)
Appendix K	Health History and Current Medications
Appendix L	Health Behaviors
Appendix M	Evaluation of Intervention
Appendix N	Change in Health Behaviors
Appendix O	Medications Updated

